3.2.1 Ophthalmologic Monitoring

At Screening, prior to Cycle 2 Day 1, and at the EOT visit, each patient will undergo a comprehensive ophthalmologic examination, with particular focus on the cornea and retina. Comprehensive ophthalmologic exams are to include fundoscopic and slit lamp exam, ocular coherence tomography (OCT), visual acuity, and review of ocular and visual symptoms.

Additionally, slit lamp examinations (with completion of fluorescein staining form) will be performed every 6 weeks after Cycle 2 Day 1 (prior to Cycle 3 Day 15, Cycle 5 Day 1, and Cycle 6 Day 15), and then every 12 weeks after Cycle 6 Day 15. Slit lamp examinations will

continue every 6–8 weeks if a patient has any persistent corneal findings. OCT is not required at these time points.

The comprehensive ophthalmologic exam will also be repeated at any point if the patient develops new visual or ocular symptoms or reports changes in visual acuity.

3.2.2 Tumor Analysis for Patient Selection

A third party laboratory in the United States will perform the FGFR2b expression and *FGFR2* amplification analysis using validated IHC and FISH assays.

Tumor tissue for FGFR2b expression and *FGFR2* amplification is optional for patients enrolling into Part 1A, and analysis may occur retrospectively.

Patients in Part 1B and Part 2 of this study must consent to tumor tissue analysis and will have their tumor tissue sent to a third party laboratory in the United States for FGFR2b expression and *FGFR2* amplification analysis. Patients may consent to tumor tissue analysis prior to consenting to enrollment in the treatment portion of this study. It is the responsibility of each Investigator to obtain an adequate tumor specimen for analysis of FGFR2b overexpression for enrollment into Part 1B and 2. Tumor slide or tumor block specimen processing, labeling, and shipping instructions are detailed in the Lab Manual that will be distributed with the specimen collection kit. For Part 1B, the first 3 gastric cancer patients enrolling into a dose cohort may have their tumor tissue analyzed retrospectively, then additional gastric cancer patients may be enrolled into that cohort if tumor tissue analysis shows FGFR2b overexpression, in the presence or absence of *FGFR2* amplification. For Part 2, once tumor specimens are received, analysis will be performed as efficiently as possible (typically within 7 calendar days of receipt), and results will be communicated back to the Investigator or designee.

For gastric cancer samples analyzed using IHC, strong FGFR2b overexpression will be defined as strong membranous staining of at least 10% of the tumor cells in a sample (scored as IHC 3+ $\geq 10\%$). For bladder cancer samples analyzed using IHC, high FGFR2b overexpression will be defined by the extent of membranous staining in tumor cells giving rise to H-score of ≥ 20 in a sample. Low FGFR2b overexpression will be defined by the extent of membranous staining in tumor cells giving rise to H-score of ≥ 10 , but < 20 in a sample. For other FGFR2b-selected non-gastric tumor types, criteria for defining FGFR2b overexpression will be determined upon availability of a validated IHC assay for each additional tumor type in question. A cohort may be closed for at any time according to the Sponsor's discretion.

Samples submitted for Part1B will be subjected to both IHC and FISH analysis (prospective or retrospectively). For Part 2, all samples from enrolled patients will be subjected to FISH retrospectively to determine *FGFR2* gene amplification (or other molecular aberrations, as relevant). For this study, a tumor will be considered *FGFR2* gene amplified if the ratio of the *FGFR2* probe to the centromeric probe (CEN10) is ≥ 2 in $\geq 10\%$ of the cells, or if there are small clusters of amplification in which the ratio cannot be determined.

[figure not shown]
3.2.3 Optional Exploratory Archival Tumor Tissue Analysis

Patients enrolled into the study (Part 1A, Part 1B, or Part 2) may elect to consent to exploratory analyses of available archival tissue samples. This exploratory analysis is distinct from the FGFR2b expression and *FGFR2* amplification analyses prescribed for patient selection in Section 3.2.2, and therefore necessitates the availability of additional archival tissue outside of that required for patient selection. The objective of this optional exploratory tumor tissue analysis is to explore the mechanism of action of FPA144 through a more thorough examination of FGFR2b signaling and immune status in the tumor. Specifically, the presence of FGFR2b fusions or mutations, the expression levels of FGFR2b and FGFR pathway genes, as well as immune cell gene signatures will be explored.

For patients who consent to the optional exploratory tumor analysis, participation is contingent upon the availability of adequate archival tumor specimens (a minimum of 1 paraffin embedded block or, in cases where a block is unavailable, approximately 10 unstained slides) and is permitted only after discussion and approval by the Sponsor. Patients may consent to exploratory tumor tissue analysis at any time after enrollment onto the treatment portion of the study. Tumor slide or tumor block specimen processing, labeling, and shipping instructions will be provided by the Sponsor upon request. Third party laboratories in the United States will perform the exploratory analyses, which will include, but are not limited to multiplex immunofluorescence, RNA sequencing, and whole exome Next Generation Sequencing (NGS).

3.3 Study Schema

Figure 3: Study Schema

3.4 Rationale for the Study Design

This is an open-label study to assess the safety, PK, PD, and preliminary efficacy of FPA144 in patients with solid tumors. The study will comprise three parts: a dose escalation portion in unselected solid tumor patients (Part 1A), a dose escalation portion in patients with gastric cancer (Part 1B), and a dose expansion portion in patients with gastric cancer and other FGFR2b-selected solid tumors, including bladder cancer (Part 2).

The 3+3 dose escalation design is standard for early stage trials of novel anticancer treatments. Dose expansion in gastric cancer and other FGFR2b-selected solid tumor patients will allow for a more thorough investigation of the safety, PK, and biological effects of FPA144 in the target population for future trials.

4. Study Eligibility and Withdrawal Criteria

4.1 Planned Number of Patients and Study Centers

Part 1A (Dose Escalation): A total of 19 patients with locally advanced or metastatic solid tumors were enrolled.

Part 1B: A total of 8 patients with gastric cancer with or without FGFR2b overexpression, in the presence or absence of *FGFR2* amplification, were enrolled.

Enrollment in Part 1(A and B) is closed as the RD for Part 2 has been determined.

Part 2 (Dose Expansion): Part 2 is open for enrollment into the following cohorts:

- Cohort A: Approximately 20 patients with gastric cancer with strong FGFR2b overexpression.
- Cohort F: Up to 30 patients with FGFR2b-selected non-gastric solid tumors (including bladder cancer for which an accompanying validated IHC assay is available). Enrollment of additional tumor types will be contingent on the development of an accompanying validated laboratory test for the analysis of FGFR2b overexpression.

The following cohorts will be closed for enrollment in Part 2:

- Cohort B: Patients with gastric cancer with FGFR2b overexpression without FGFR2 amplification
- Cohort C: Patients with gastric cancer without FGFR2b overexpression
- Cohort D: Patients with gastric cancer with moderate FGFR2b overexpression
- Cohort E: Patients with gastric cancer with low FGFR2b overexpression

The study will be conducted at up to 35 investigational centers globally.

4.2 Inclusion Criteria for Study Participation

Patients enrolling into Part 1(A and B) or Part 2 must meet *all* of the following inclusion criteria:

1. Understand and sign an Institutional Review Board/Independent Ethics Committee-approved informed consent form prior to any study-specific evaluation
2. Life expectancy of at least 3 months
3. ECOG performance status of 0 to 1
4. Age ≥ 18 years at the time the informed consent form is signed except for the patients in Taiwan, where the patient's age must be ≥ 20 at the time the informed consent form is signed
5. In sexually-active patients (i.e., females of childbearing potential, who have not undergone menopause as defined by 12 consecutive months of amenorrhea or had a permanent sterilization procedure and males, who have not had a permanent sterilization procedure), willingness to use 2 effective methods of contraception, of which one must be a physical barrier method (condom, diaphragm, or cervical/vault cap) until 6 months after the last dose of FPA144. Other effective forms of contraception are permanent sterilization (hysterectomy and/or bilateral oophorectomy, or bilateral tubal ligation with surgery, or vasectomy) at least 6 months prior to Screening. Female patients of childbearing potential must be on stable oral contraceptive therapy or intrauterine or implant device for at least 90 days prior to the study, or abstain from sexual intercourse as a way of living
6. Adequate hematological and biological function, confirmed by the following laboratory values:
 - a) Bone marrow function
 - ♦ $ANC \geq 1.5 \times 10^9/L$
 - ♦ Platelets $> 100 \times 10^9/L$
 - ♦ Hemoglobin ≥ 9 g/dL
 - b) Hepatic function
 - ♦ AST and ALT ≤ 3 x upper limit of normal (ULN); if liver metastases, then ≤ 5 x ULN
 - ♦ Bilirubin ≤ 1.5 x ULN
 - c) Renal function
 - ♦ Serum creatinine ≤ 1.5 x ULN
7. Tumor tissue, must be available for determination of FGFR2b overexpression (*optional for Part 1A patients*)

4.2.1 Part 1A (Dose-Escalation)

Patients enrolling in this portion of the study must also meet the following inclusion criteria:

8. Histologically or cytologically confirmed solid tumor or lymphoma that is locally recurrent or metastatic and has progressed following standard treatment or is not appropriate for standard treatment
9. Measurable or non-measurable disease

4.2.2 Part 1B

Patients enrolling in this portion of the study must also meet the following inclusion criteria:

10. Histologically documented gastric or gastroesophageal cancer
11. Tumor tissue for prospective or retrospective determination of FGFR2b expression and *FGFR2* amplification
12. Locally recurrent or metastatic disease that has progressed on or following standard treatment, or is not a candidate for standard treatment
13. Measurable disease as defined by RECIST version 1.1

4.2.3 Part 2 (Dose-Expansion)

Patients enrolling in this portion of the study must also meet the following inclusion criteria:

14. The following tumor types, by cohort:
 - Cohort 2A: Histologically documented gastric or gastroesophageal cancer with FGFR2b overexpression, as determined by an accompanying, validated IHC assay
 - Cohort 2F: Histologically or cytologically confirmed bladder cancer (including tumors of the renal pelvis, ureters, urinary bladder, or urethra), or other histologically or cytologically confirmed solid tumor types with FGFR2b overexpression, as determined by an accompanying validated laboratory test for the analysis of FGFR2b expression
15. Tumor tissue for prospective determination of FGFR2b expression and retrospective determination of *FGFR2* amplification and other molecular aberrations (as applicable)
16. Locally recurrent or metastatic disease that has progressed on or following standard treatment, or is not a candidate for standard treatment
17. Measurable disease as defined by RECIST version 1.1

Exclusion Criteria for Study Participation

Patients enrolling into Part 1(A and B) or Part 2 will be excluded if any of the following criteria apply:

1. Untreated or symptomatic central nervous system (CNS) metastases. Patients with asymptomatic CNS metastases are eligible provided they have been clinically stable for at least 4 weeks and do not require intervention such as surgery, radiation, or any corticosteroid therapy for management of symptoms related to CNS disease

2. Impaired cardiac function or clinically significant cardiac disease, including either of the following:
 - a) Unstable angina pectoris ≤ 6 months prior to first scheduled dose of FPA144
 - b) Acute myocardial infarction ≤ 6 months prior to first scheduled dose of FPA144
3. QTc segment > 470 msec
4. Known HIV or AIDS-related illness, or history of chronic hepatitis B or C
5. Treatment with any anticancer therapy or participation in another therapeutic clinical study with investigational drugs ≤ 14 days (≤ 28 days for patients in Korea) prior to first dose of FPA144
6. Ongoing acute adverse effects from such treatment $>$ NCI CTCAE Grade 1
7. Retinal disease or a history of retinal disease or detachment or, in the ophthalmologist's opinion, at increased risk for retinal detachment
8. Corneal defects, corneal ulcerations, keratitis, keratoconus, history of corneal transplant, or other known abnormalities of the cornea that may, in the opinion of an ophthalmologist, pose a risk with FPA144 treatment
9. NSCLC patients with exon 19 or 21 EGFR mutation or ALK amplification who have not received an EGFR or ALK TKI, respectively (*Part 1A only*)
10. Gastric and breast cancer patients with HER2 overexpression who have not received anti-HER2 targeted therapy
11. Major surgical procedures are not allowed ≤ 28 days prior to FPA144 administration. In all cases, the patient must be sufficiently recovered and stable before treatment administration
12. Females who are pregnant or breastfeeding; women of childbearing potential must not be considering getting pregnant during the study
13. Presence of any serious or unstable concomitant systemic disorder incompatible with the clinical study (e.g., substance abuse, psychiatric disturbance, or uncontrolled intercurrent illness including active infection, arterial thrombosis, and symptomatic pulmonary embolism)
14. Presence of any other condition that may increase the risk associated with study participation or may interfere with the interpretation of study results, and, in the opinion of the Investigator, would make the patient inappropriate for entry into the study
15. Known allergy or hypersensitivity to components of the FPA144 formulation including polysorbate
16. History of prior malignancy except:
 - a) Curatively treated non-melanoma skin cancer or

- b) Solid tumor treated curatively more than 5 years previously without evidence of recurrence or
- c) History of other malignancy that in the Investigator’s opinion would not affect the determination of study treatment effect

4.2.4 Additional Part 1B and Part 2 (Dose Expansion) Exclusion Criteria

17. Prior treatment with any selective inhibitor (e.g., AZD4547, BGJ398, JNJ-42756493, BAY1179470) of the FGF-FGFR pathway

No waivers of these inclusion or exclusion criteria will be permitted.

4.3 Patient Withdrawal and Replacement

The patient has the right to stop treatment or to withdraw from the study at any time. Patients may continue to repeat cycles of FPA144 treatment until at least one of the following criteria applies:

- Consent withdrawal at the patient’s request or at the request of their legally authorized representative
- Progression of patient’s underlying disease. Patients who are receiving clinical benefit despite isolated disease progression may continue on study after discussion with Medical Monitor
- Any event that would pose an unacceptable safety risk to the patient
- An intercurrent illness that would affect assessments of the clinical status to a significant degree and require discontinuation of therapy
- A positive pregnancy test at any time during the study
- At the specific request of the Sponsor or its authorized representative (for example, if the study is terminated for reasons of patient safety)

The date and reason for cessation of FPA144 will be documented, and the Investigator must make every effort to perform the EOT procedures. Patients will be followed for 28 days after the last dose of FPA144 for safety; those with ongoing SAEs will be followed until either resolution or stabilization.

Data from patients who discontinue prematurely will remain part of the study database. Withdrawn patients at a given dose level may be replaced at the discretion of the Sponsor.

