The MTD is defined as the highest dose associated with DLTs in less than 33% of patients receiving FPA144 administered on Days 1 and 15 of a 28-day cycle. This will normally be the dose recommended for further study (RD); however, based on review of safety and PK data, the RD could be lower than the MTD. If the MTD is not reached, and the highest evaluated FPA144 dose is well tolerated, the data will be reviewed to assess whether further dose escalations are warranted. The protocol will be amended if additional dose escalation is considered appropriate.

If the MTD is not reached during Part 1A, or subsequent cycles of treatment in Part 1A provide additional insight on the safety profile, an RD may be selected based on overall tolerability, safety, and PK.

If a patient does not receive 2 doses and does not complete the safety and PK assessment in Cycle 1 for reasons other than toxicity (e.g., disease progression or withdrawal of consent), then an additional patient will be enrolled into the cohort so that the cohort has at least three patients evaluable for tolerability through Cycle 1. All such discussions and decisions will be documented as part of the dose escalation decision-making process.

Intra-patient dose escalation above the starting dose for each patient will not be permitted for patients in Part 1 (A and B) and Part 2. If a patient's dose is decreased for a reason that is no longer relevant, dose escalation to the originally assigned dose may occur after discussion and approval by the Sponsor.

On completion of Cycle 1 (Safety and PK Assessment Period), Part 1A patients may participate in an optional Treatment-Extension Period, which begins on Day 1 of Cycle 2. FPA144 will be administered once every 2 weeks until disease progression, unacceptable toxicity, patient or physician decision to discontinue, death, or termination of the study (as defined in Section 9.11), assuming no limitations with availability of drug supply, or other issues that may preclude the Sponsor from providing FPA144.

Enrollment into Part 1A is complete. A total of 19 patients with solid tumors were enrolled into Part 1A before its closure in November of 2015.

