8.10 Determination of Sample Size

Three patients per dose group, with a sample size increase to 6 in the case of DLT, is generally accepted as adequate to determine the safety of escalating doses of novel oncologic drugs. If a DLT is observed in 1 of 3 patients, then 3 additional patients will be enrolled at that same dose level. Dose escalation will continue until 2 of 3–6 patients treated at a dose level experience a DLT. The maximum tolerated dose (MTD) is defined as the maximum dose at which < 33% of patients experience a DLT during Cycle 1. After the MTD is determined, additional gastric cancer patients may be recruited at that dose level to further characterize the safety, PK, pharmacodynamics, and preliminary efficacy of FPA144.

In Part 1B, up to 30 patients with gastric cancer with or without FGFR2b overexpression, in the presence or absence of *FGFR2* amplification may be enrolled to explore preliminary long-term safety and PK.

In each of the Part 2 gastric cancer cohorts (Cohorts A, C, D, and E), approximately 30 gastric cancer patients with ranges of FGFR2b overexpression scores (IHC 3+ \geq 10%; IHC 0; IHC 2+ \geq

10% tumor membrane staining **and/or** IHC 3+ < 10%; IHC 1+ **and/or** IHC 2+ < 10%) will be enrolled and treated to further characterize safety and preliminary efficacy. For each cohort, a response rate of $\geq 20\%$ would be considered clinically meaningful. To ensure adequate efficacy, an interim analysis may be performed (with the assumption that a response rate of $\leq 5\%$ would be of no interest in the first stage). Assuming a significance level of 5% and 80% power (Table 5), the required sample size is 29 evaluable patients per cohort. The Sponsor may choose to suspend enrollment if no confirmed response (CR or PR) is observed after the first 10 evaluable patients have either received at least 4 cycles of therapy or have had disease progression, as it is unlikely the response rate would be 20% or more. If a full cohort of 30 patients is enrolled for a group, the precision of the 95% confidence interval for the response rate is within 18%.

Table 6: Parameters of Simon’s 2-stage Design

Targeted Response Rate	Response Rate of No Interest	Overall Sample Size	Sample Size at Stage I	Responses to go to Stage II	Number of Overall Responses
20%	5%	29	10	≥ 1	≥ 4

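### In Part 2, dosed patients who fail before their first post-baseline assessment can leave the response denominator and be replaced at the Sponsor's discretion, which can bias the ORR and the 10/29 decision upward.

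*Combined protocol and SAP*

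**What the plan says.** Section 4.3 lists the circumstances that end treatment. They include progression of the underlying disease and "Any event that would pose an unacceptable safety risk to the patient". The section keeps the data of patients who stop early in the study database, and then adds: "Withdrawn patients at a given dose level may be replaced at the discretion of the Sponsor". It does not restrict replacement by reason, by timing, by whether the patient was dosed, or by study part. No other section gives a replacement rule for Part 2.

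For Part 1A, Section 3.1.2 deals with patients who do not complete Cycle 1 "for reasons other than toxicity (e.g., disease progression or withdrawal of consent), then an additional patient will be enrolled into the cohort".

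Section 8.1.3 defines the Efficacy-Evaluable Population as eligible patients with at least one dose, measurable lesions at baseline and at least one disease assessment after baseline.

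Section 8.10 sets out a Simon two-stage design for a 5% versus a 20% response rate. "Assuming a significance level of 5% and 80% power", it says, "the required sample size is 29 evaluable patients per cohort". Table 6 gives 10 patients at stage 1, at least 1 response to continue, and at least 4 responses overall. The same design is to guide each tumor type in Cohort F. Section 4.1 now puts Cohort A at about 20 patients and Cohort F at up to 30.

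**The concern.** Each provision is ordinary when read alone. Together they open a path by which failures leave the count. The first scheduled scan is about six weeks after the first dose (Section 6.1). A dosed patient who dies, deteriorates clinically or stops for toxicity before then may have no post-baseline assessment. That patient is outside the evaluable set and is also a withdrawn patient whom the Sponsor may replace. The study is open-label, so the reason for leaving is known when the decision is taken.

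Every such patient is a non-responder. If they are removed and the cohort is refilled, the response rate is computed on a set selected partly on outcome, and both the stage 1 look at 10 and the final count at 29 use that set. What is at stake is the reported ORR, a secondary objective, and the decision whether a tumor type looks active enough to pursue.

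**Working it through.** **Inputs.** From Section 8.10 and Table 6: null rate 5%, target rate 20%, level 5%, power 80%, n1 = 10, at least 1 response to continue, n = 29, at least 4 responses for success. The documents give no share of early failures, so w = 5%, 10% and 20% of dosed patients are assumptions.

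**Step 1. Reproduce the plan's design.** With response probability p per counted patient and the stage 1 stop applied:

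P(success) = sum over x = 1, 2, 3 of P(X1 = x) × P(X2 ≥ 4 − x) + P(X1 ≥ 4), where X1 ~ Bin(10, p) and X2 ~ Bin(19, p).

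At p = 0.05:
- x = 1: 0.3151 × 0.0665 = 0.0210
- x = 2: 0.0746 × 0.2453 = 0.0183
- x = 3: 0.0105 × 0.6226 = 0.0065
- x ≥ 4: 0.0010
- total 0.0468

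At p = 0.20 the total is 0.801. The design therefore meets its stated level and power. A search over two-stage designs returns it as Simon's optimal design.

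**Step 2. Remove uncounted early failures.** If a share w of dosed patients are non-responders who leave the count and are replaced, the response probability per counted patient is p / (1 − w). Put this into the Step 1 formula with n = 29:

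| w | 0.05 / (1 − w) | false-positive rate | 0.20 / (1 − w) |
|---|---|---|---|
| 0 | 0.0500 | 0.0468 | 0.200 |
| 5% | 0.0526 | 0.0546 | 0.211 |
| 10% | 0.0556 | 0.0641 | 0.222 |
| 20% | 0.0625 | 0.0898 | 0.250 |

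**Step 3. Patients needed.** Reaching 29 counted patients takes 29 / (1 − w) dosed patients: 30.5, 32.2 and 36.3, or about 31, 32 and 36.

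**Step 4. Cohort A at 20.** With at least 4 responses of 20 and the same stage 1 rule, the false-positive rate is 0.015 with no removals, and 0.018, 0.022 and 0.032 for w = 5%, 10% and 20%. It stays below 5%. The inflation of the ORR is the same as in the last column of the table.

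**Step 5. Does the end-of-treatment scan close the gap?** Only in part. Section 7.2.11 schedules that visit about 28 days after the last infusion, and the scan may be omitted if the previous one is less than 6 weeks old or if progression was already determined. After a single dose, a screening scan taken less than 42 − 28 = 14 days before dosing would permit the omission. A patient who dies has no such visit.

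**The case against.** The strongest reply is that the plan already keeps most failures. A patient with progression on a scan meets the Section 8.1.3 definition, and Section 8.10 counts patients with progression among the first 10. Clinical progression is also one of the progression criteria in Section 6.1, so some early clinical progressors might be judged evaluable, although Section 8.1.3 does not say so. All of this stands, and it confines the problem to patients with no post-baseline assessment. The sentence on retaining data does not close that gap, because keeping data in a database does not define a denominator.

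The reference to a given dose level sounds like dose-escalation wording. That is fair, but Part 2 is not excluded and is treated at one recommended dose.

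Efficacy is descriptive (Section 8.7), no formal interim efficacy analysis is planned (Section 8.9), and a separate SAP is to follow. So the harm is a biased estimate and a biased go/no-go reading, not a failed confirmatory test.

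Three stronger readings are tempting, and the documents do not support them:
- A reader might infer that replacing any progressor destroys the 5% level. That does not follow, because scanned progressors stay in the count. If the rule is read on the first 29 patients with every failure included, the level stays at 4.7%.
- A reader might add replacements on top of 29 while keeping the threshold at 4, which gives 7.0% at 34 patients and 9.6% at 39. Table 6 ties the 4-response rule to 29, and both sizes exceed the open cohorts. At Cohort F's limit of 30 the figure would be 5.1%.
- A reader might say that Section 3.1.2 permits replacement only for non-toxicity reasons, so that Section 4.3 contradicts it. Section 3.1.2 requires an additional patient in that case and is silent on toxicity. The wording differs and should be aligned, but Part 1A is closed and had no DLTs.

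The level is also not exact for another reason. The stage 1 stop is optional, and ignoring it gives 5.5% at 29 patients with no replacement at all.

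**Conclusion.** The concern holds in a limited form. Sections 4.3, 8.1.3 and 8.10 together allow dosed Part 2 patients who fail before any post-baseline assessment to be left out of the response count and replaced, and the resulting bias in the ORR is upward. For a cohort run to 29 counted patients, such as a Cohort F tumor type, early-failure shares of 5%, 10% and 20% move the false-positive rate from 4.7% to 5.5%, 6.4% and 9.0%. A true ORR of 20% would read as about 21%, 22% and 25%.

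These figures assume that the stage 1 stop is applied, that all such patients are replaced, and that replacements do not count against Cohort F's limit of 30, a point on which the documents are silent. If they do count, at most one early failure can be replaced in a cohort that reaches 29. For Cohort A at about 20 patients the concern is ORR bias alone. The change should be made, but nothing confirmatory depends on it.

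**What to change.** Amend Sections 4.3 and 8.10 to state that, in Part 2:
- only patients who were enrolled but never dosed are replaced;
- every dosed patient with measurable disease at baseline stays in the response denominator, as a non-responder if there is no post-baseline assessment;
- any patients added do not displace earlier ones;
- the 10- and 29-patient decisions use the first 10 and 29 such dosed patients in enrollment order. The stage 1 completion condition should then also cover a patient who dies or stops without an assessment.

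The evaluable-set ORR from Section 8.1.3 can be kept as a supportive analysis. Separately, reconcile the replacement wording of Section 4.3 with Section 3.1.2 for Part 1A.

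With the set fixed and the stage 1 stop applied, the false-positive rate at 29 patients returns to 4.7% and power to 80.1%. The cost is a few sentences in an amendment. The small downside is that the reported ORR may be slightly lower and a cohort may have slightly fewer scan-evaluable patients.
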